1.0 Study Summary

Study Title	Comparative evaluation of lumbar plexus and suprainguinal fascia iliaca compartment block for pain management after orthopedic surgical procedures involving hip and femur in pediatrics.
Study Design	Prospective study
Primary Objective	The primary objective will be to measure total time to perform the regional anesthesia technique.
Secondary Objective(s)	The secondary objectives are opioid consumption during the first 24 and 48 postoperative hours, pain scores during the first 24 and 48 hours, and hospital length of stay.
Research Intervention(s)/Investigational Agent(s)	Lumbar plexus block or fascia iliaca compartment block with ropivacaine 0.5% with 1:200,000 epinephrine.
IND/IDE #	N/A
Study Population	Patients undergoing elective orthopedic surgical procedures involving the hip and upper thigh.
Sample Size	70
Study Duration for individual participants	Time of surgery to discharge home - ~ 48 hours
Study Specific Abbreviations/Definitions	LPB – lumbar plexus block FICB – fascia iliaca compartment block

2.0 Objectives

- 2.1 The primary objective will be to measure total time to perform the regional anesthesia technique. The secondary objectives are opioid consumption during the first 24 and 48 postoperative hours, pain scores during the first 24 and 48 hours, and hospital length of stay.
- 2.2 The hypothesis is that the two techniques will be equally effective in providing analgesia following hip and femur surgery in the pediatric population; however, the time to perform the FICB will be shorter than the lumbar plexus block.

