3.0 Background

- 3.1 Regional anesthesia techniques including peripheral nerve blockade in children undergoing orthopedic procedures provide effective postoperative analgesia, reduce opioid consumption, decrease the time to discharge, and minimize the exposure to general anesthetic agents.¹⁻³ Increased use of regional anesthesia in infants, children, and adolescents has significantly improved the scope of pediatric pain management. Epidural analgesia was formerly the gold standard for

PROTOCOL TITLE: LPB vs FICB

pain treatment following orthopedic procedures involving the lower extremities despite the potential for adverse effects including hypotension and urinary retention. Additionally, epidural analgesia provides bilateral sensory blockade for what may be a unilateral procedure. Lumbar plexus blockade (LPB) has recently seen increased use as an adjunct to decrease opioid consumption for procedures involving the hip and thigh.^{3,4} However, the technique is complex, time-consuming, and is associated with potential complications including needle advancement into the peritoneum or retroperitoneum, which may result in a renal hematoma, vascular puncture (retroperitoneal hematoma), or even bowel puncture.

Alternatively, fascia iliaca compartment block (FICB) provides an easy and safe technique to anesthetize the femoral, lateral femoral cutaneous, and obturator nerves in a superficial fascial plane avoiding the potential risks of lumbar plexus block.⁵ FICB reduces opioid consumption in adult patients after total hip arthroplasty. Desmet et al. demonstrated that a supra-inguinal FICB reduced opioid consumption by 46% in the first 24 hours and 45% over 48 hours in adult patients following total hip arthroplasty thus offering another regional anesthetic technique to provide postoperative pain management following procedures on the hip and upper thigh.⁶ To our knowledge, there are no studies comparing lumbar plexus block to fascia iliaca block for pain management after orthopedic procedures involving the hip and femur in the pediatric population.

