- 3.2 We aim to compare the use of a suprainguinal FICB vs lumbar plexus block as an adjunct to general anesthesia in pediatric patients undergoing orthopedic procedures involving the hip or upper femur. This study will help determine the efficacy of the two techniques and their advantages when compared to each other including time to perform the block, opioid consumption reduction, effects on postoperative pain, and the length of stay. If the FICB technique is equally effective, it would offer a safer alternative to lumbar plexus block, which may be accomplished in a more expeditious manner.

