4.0 Study Endpoints

- 4.1 Time to perform each block.
- 4.2 Pain scores and opioid consumption during the first 24 and 48 hours post-op.

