6.0 Procedures Involved*

- 6.1 This will be a double-blinded, randomized, prospective study involving patients, ranging in age between 2 and 18 years of age, ASA grade I-III, undergoing elective orthopedic surgical procedures involving the hip and upper thigh. Patients will be randomly divided into 2 groups: Group LP and Group FICB. The block (LP or FICB) will be performed by one of the study investigators. The team providing intraoperative care will step out of the room during the regional block and care will be provided by the research team including an attending anesthesiologist. Once the primary anesthesia team finishes the induction phase, the study team will perform the regional anesthesia time-out. Measurement of the time to complete the block will start when the time-out is completed and end when the need is withdrawn and the patient is positioned in the surgical positioning. The perioperative care teams will be blinded to the type of the block by using two dressings in all the patients. The first dressing will be placed at the actual site of needle insertion and the second dressing at the site where needle would have been inserted if the patient were to receive the other type of block (in the back for the LP block and groin for the FICB).

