10.1 Potential subjects will be identified by reviewing the surgery schedule in Epic and will be recruited from the Surgery Unit pre-op area prior to their surgery.

10.2 Inclusion criteria: Aged 2-18 years, ASA grade 1-3, undergoing elective orthopedic surgical procedures involving the hip and upper thigh.

Exclusion criteria: Local anesthetic allergy, skin or localized infection at the site of catheter insertion opioid use within 3 months prior to surgery, history of opioid abuse or dependence, pre-existing motor or sensory deficits, patient or parent refusal.

10.3 We are including children, and will not include:

- Adults unable to consent
- Pregnant women
- Prisoners

11.0 **Vulnerable Populations***

11.1 This study presents no more than minimal risk as it involves regional nerve blocks which are used routinely as standard of care by the anesthesiologists at this institution.

12.0 **Local Number of Subjects**

12.1 70

12.2 Sample size will be determined according to a previous study investigating the time taken to perform 2 variations on the lumbar plexus block, with the slower technique taking 334 ± 156 seconds and the faster technique taking 238 ± 74 seconds. We hypothesize that the time difference between the 2 techniques in our study will be

PROTOCOL TITLE: LPB vs FICB

at least as large as the difference between the 2 block types investigated in this prior study. Specifically, assuming that the FICB will be at least 96 seconds faster than the LP block while the pooled standard deviation is 128 seconds, the proposed t-test would have 80% power to confirm a statistically significant difference at a 95% confidence level when at least 29 subjects are enrolled in each group. Therefore, we propose enrolling a total of 70 patients to account for dropout or missing data.

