17.0 Data Management* and Confidentiality

17.1 Continuous outcomes will be compared between groups using 2-sample t-test or rank-sum tests according to the normality of the distribution (checked by the Shapiro-Wilk test). Categorical outcomes will be compared between groups using Chi-square or Fisher's exact tests, according to cell size.

17.2 Research records will be stored in a locked cabinet and password protected computer. Only certified research personnel will be given access to identifiable subject information

PROTOCOL TITLE: LPB vs FICB

17.3 Following publication of study results, research records will be stored for a period of 3-5 years and then will be destroyed by placing in a secure shredding bin.

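### Section 2.2 hypothesises equal analgesia, but section 17.1 plans only tests of difference, with no estimate, confidence interval or margin for the analgesic outcomes

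*Combined protocol and SAP*

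**What the plan says.** Section 2.2 gives one hypothesis in two parts. On analgesia: "The hypothesis is that the two techniques will be equally effective in providing analgesia following hip and femur surgery". On speed, FICB is expected to take less time than LPB.

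Block time is the primary objective. The analgesic outcomes are secondary: "The secondary objectives are opioid consumption during the first 24 and 48 postoperative hours, pain scores during the first 24 and 48 hours" (2.1). Section 4.2 lists the same outcomes as endpoints: "Pain scores and opioid consumption during the first 24 and 48 hours post-op".

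Section 17.1 is the only place that says how outcomes will be compared: "Continuous outcomes will be compared between groups using 2-sample t-test or rank-sum tests according to the normality of the distribution". Categorical outcomes get a chi-square or Fisher's exact test.

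Section 12.2 bases the sample size on block time alone, "assuming that the FICB will be at least 96 seconds faster than the LP block while the pooled standard deviation is 128 seconds", which gives 29 per group and 70 enrolled to allow for losses. The 95% confidence level mentioned there is the significance level of that t-test, not a planned interval.

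Section 3.2 links analgesia to the study's rationale: "If the FICB technique is equally effective, it would offer a safer alternative to lumbar plexus block".

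**The concern.** The two parts of the hypothesis need different evidence. A test of difference suits the speed part, because rejecting the null hypothesis supports the claim. It does not suit the analgesia part. There equality is the null hypothesis, and failing to reject it may mean that the blocks are alike or only that the data are imprecise. A p-value does not tell these apart. An estimate with its CI does, because it shows how large a loss of analgesia remains possible.

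I found no commitment in any section to a between-group estimate, a CI, a margin or a rule for reading the analgesic results. As written, the plan can produce evidence against this part of its hypothesis but none for it.

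This matters for the argument in 3.2. The safety premise comes from the background in 3.1, which describes FICB as "avoiding the potential risks of lumbar plexus block"; safety is not among the trial's endpoints. What the trial itself can add is a comparison of speed, which is properly tested, and a comparison of analgesia. Section 3.1 also says that the authors know of no pediatric comparison of these two blocks, so readers would have little else to turn to.

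**Working it through.** **1. The plan's own figure.** Inputs from 12.2: difference 96 s, SD 128 s, 80% power, 95% confidence level (taken as two-sided 0.05). Standardised difference = 96/128 = 0.75. The noncentral-t solution is 28.9, so 29 per group, with power 0.801. The stated 29 reproduces; a one-sided test would need only about 23. The primary sample size is sound on its own inputs.

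**2. Inputs for analgesia.** The documents give no SD and no meaningful difference for opioid use or pain scores. I therefore work in SD units and assume roughly normal data and equal groups: n = 29 (the number required) or n = 35 (70/2, no losses). The true differences of 0.3 and 0.5 SD and the margin of 0.5 SD are illustrative choices.

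**3. Precision.** 95% CI half-width = t(0.975, 2n−2) × √(2/n).
- n = 29: 2.003 × 0.2626 = 0.526 SD
- n = 35: 1.996 × 0.2390 = 0.477 SD

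If the observed difference were exactly zero, the CI would still reach about half an SD in each direction.

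**4. How often a real disadvantage would be non-significant.** Noncentrality = d/√(2/n); the share is 1 − power of the two-sided t-test.

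| True FICB disadvantage | n = 29 | n = 35 |
|---|---|---|
| 0.3 SD | 0.798 | 0.764 |
| 0.5 SD | 0.535 | 0.459 |

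Non-significance would thus be a common result even if FICB were worse by half an SD.

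**5. What a formal similarity claim could achieve.** Margin 0.5 SD, no true difference:
- Non-inferiority (one-sided 0.025): probability of success 0.465 at n = 29 and 0.541 at n = 35.
- Equivalence (two one-sided tests, 90% CI, margin ±0.5 SD): about 0.19 and 0.33.
- An 80% chance would need about 64 per group for non-inferiority or 70 for equivalence.

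All these figures are approximate for skewed opioid data.

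**The case against.** The strongest reply is that these are secondary outcomes and no harm is planned. The trial is sized for block time, and that comparison is correct. The analgesia sentence in 2.2 can be read as an expectation, which a difference test can refute. The sentence in 3.2 is conditional and sits in the background, so it is not a decision rule. Naming tests in 17.1 does not rule out reporting estimates, and a CI can be computed from the same data at any time.

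Most of this stands, and it limits the point. It does not remove it: an outcome named in the hypothesis needs a planned result that could bear on it, and a test of difference alone is not one. That a CI could be computed later is not a commitment to report it, nor a rule for reading it.

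A reader might infer more than the documents support:
- *That the investigators will read p > 0.05 as equality.* No section says so.
- *That precision for analgesia was ignored.* Section 12.2 shows only that none is documented, and sizing on the primary outcome is ordinary.
- *That a non-significant result leaves a loss of about 1 SD open.* The upper limit approaches twice the half-width (1.05 SD at n = 29, 0.95 SD at n = 35) only when p is just above 0.05. At an observed difference of zero it is 0.53 or 0.48 SD.
- *That half an SD is clinically important here.* Nothing in the documents establishes that.

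One practical objection also stands. A CI needs a defined outcome. Sections 6.3 and 6.4 use three pain instruments with repeated assessments, and both hydromorphone and oxycodone, without stating a per-patient pain summary or a common opioid unit. The fix has to supply these.

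**Conclusion.** The point holds as a cheap improvement. The tests in 17.1 cannot support the analgesia part of 2.2, and no section commits to an estimate, CI or margin that could. With roughly normal data and 29 (35) per group, the 95% CI half-width is about 0.53 (0.48) SD, and a true FICB disadvantage of 0.5 SD would be missed in about 54% (46%) of trials. A non-significant p-value would therefore be weak evidence of equality.

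The gap in 17.1 is plain from the text and depends on no assumption. The sizes rest on the SD-unit assumption and would need restating once real SDs are known. The point does not extend to the block-time comparison, to the sample size, or to the conditional wording in 3.2.

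**What to change.** Add to 17.1:

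> For 24 h and 48 h opioid consumption (in one common opioid unit, per kg) and pain score (one stated per-patient summary for each period, on a common 0-10 range), the FICB minus LPB difference will be reported with a two-sided 95% CI (Hodges-Lehmann or bootstrap if skewed). A non-significant p-value will not be taken as evidence of equal effectiveness.

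State which pain summary and which opioid conversion will be used. Reword 2.2 so that analgesia is compared by estimate and 95% CI, rather than hypothesised to be equal. Section 3.2 needs no edit.

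Optional: if the sponsor wishes to claim similarity, set a margin before any outcome data are examined. A cut-off at unblinding would not serve, because "The block (LP or FICB) will be performed by one of the study investigators" (6.1), so some investigators know the allocation from the start. At this size such a claim is unlikely to succeed: at the illustrative 0.5 SD margin with no true difference, the chance is 46-54% for non-inferiority and 19-33% for equivalence.

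Cost: a few sentences, the outcome definitions and a little extra analysis of data already collected. No patients are added, and treatment and the primary analysis do not change. The downside is that the trial may be unable to claim equal analgesia.

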3.0 Background

- 3.1 Regional anesthesia techniques including peripheral nerve blockade in children undergoing orthopedic procedures provide effective postoperative analgesia, reduce opioid consumption, decrease the time to discharge, and minimize the exposure to general anesthetic agents.¹⁻³ Increased use of regional anesthesia in infants, children, and adolescents has significantly improved the scope of pediatric pain management. Epidural analgesia was formerly the gold standard for

PROTOCOL TITLE: LPB vs FICB

pain treatment following orthopedic procedures involving the lower extremities despite the potential for adverse effects including hypotension and urinary retention. Additionally, epidural analgesia provides bilateral sensory blockade for what may be a unilateral procedure. Lumbar plexus blockade (LPB) has recently seen increased use as an adjunct to decrease opioid consumption for procedures involving the hip and thigh.^{3,4} However, the technique is complex, time-consuming, and is associated with potential complications including needle advancement into the peritoneum or retroperitoneum, which may result in a renal hematoma, vascular puncture (retroperitoneal hematoma), or even bowel puncture.

Alternatively, fascia iliaca compartment block (FICB) provides an easy and safe technique to anesthetize the femoral, lateral femoral cutaneous, and obturator nerves in a superficial fascial plane avoiding the potential risks of lumbar plexus block.⁵ FICB reduces opioid consumption in adult patients after total hip arthroplasty. Desmet et al. demonstrated that a supra-inguinal FICB reduced opioid consumption by 46% in the first 24 hours and 45% over 48 hours in adult patients following total hip arthroplasty thus offering another regional anesthetic technique to provide postoperative pain management following procedures on the hip and upper thigh.⁶ To our knowledge, there are no studies comparing lumbar plexus block to fascia iliaca block for pain management after orthopedic procedures involving the hip and femur in the pediatric population.

- 3.2 We aim to compare the use of a suprainguinal FICB vs lumbar plexus block as an adjunct to general anesthesia in pediatric patients undergoing orthopedic procedures involving the hip or upper femur. This study will help determine the efficacy of the two techniques and their advantages when compared to each other including time to perform the block, opioid consumption reduction, effects on postoperative pain, and the length of stay. If the FICB technique is equally effective, it would offer a safer alternative to lumbar plexus block, which may be accomplished in a more expeditious manner.

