6.3 Postoperative analgesia will be achieved with IV hydromorphone as needed (PRN) with a dose regimen of 0.02 mg/kg per dose. Depending on patient's use if there is need to escalate treatment a PCA, NCA or CCA will be started. Patients will also receive IV acetaminophen 15 mg/kg every 6 hours and IV ketorolac 0.5 mg/kg every 6 hours (unless contraindicated) during the 48 hour study period. The first dose of these two agents will be administered in the operating room at the completion of the surgical procedure. If the patient is ready to transition from IV to oral pain medications, oxycodone (0.1 mg/kg every 4 hours) will be started and the hydromorphone discontinued. At that time, acetaminophen will be switched to oral and ketorolac switched to oral ibuprofen.

6.4 The following data will be collected:

- Block procedure time (in minutes and seconds)
- Opioid administration intraoperatively.
- Postoperative opioid consumption in the PACU.
- Postoperative opioid consumption for the first 48 hours after surgery (PACU discharge to inpatient ward admission).
- Pain assessment scores (VAS in older children, FACES scales in children between 2-4 and FLACC for non-verbal children) in the PACU (first pain score) and for the first 48 hours (standard pain assessments) on the inpatient ward.
- The duration of the need for intravenous opioid therapy.
- Use of rescue pain medications in the PACU, on the floor, including non-opioids, will also be recorded and analyzed.
- Hospital length of stay.

The following demographic and surgical parameters will also be collected and recorded: patient age, gender, race/ethnicity, height, weight, ASA status, primary diagnosis, list of comorbidities, procedure, date, duration, admission status intraoperative medications, PACU arrival and discharge times, discharge destination, pain scores (including recorded time),

PROTOCOL TITLE: LPB vs FICB

regional anesthetic time and dose, and time of hospital admission and discharge.

7.0 **Data and Specimen Banking***

N/A

8.0 **Sharing of Results with Subjects***

8.1 Results will not be shared.

9.0 **Study Timelines***

- An individual study subject's participation in the study should last approximately 48 hours total.
- All study subjects should be enrolled within 2 years of study start.
- The study should be completed within 3 years of study start.

10.0 **Inclusion and Exclusion Criteria***

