15.0 Risks to Subjects*

15.1 The common side effects of ropivacaine (the numbing medication used in the nerve blocks) are injection site burning or pain and prickly feeling as the block wears off. Occasional side effects of ropivacaine are ear ringing, metallic taste, and drowsiness. Rare side effects of ropivacaine are seizures, unconsciousness, respiratory arrest, low blood pressure, irregular heartbeat, cardiac arrest, and allergic reactions including anaphylaxis. There is also potential risk for loss of confidentiality.

15.2 Subject information will not be given to any other investigators. Subjects and their information will be closely monitored and guarded by study staff; there will be limited access to patients and their information by trained study staff; and subject information will only be shared and discussed between study staff specific to this study. Subject PHI will be stored in a locked cabinet, and will be stored and maintained in password protected computer files.

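### The rationale calls FICB a safer alternative, but the trial records no block complications or failed blocks, and the risk section omits the needle-related LPB risks named in the Background

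*Combined protocol and SAP*

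**What the plan says.** Section 3.2 closes the Background with a conditional statement: should FICB prove equally effective, "it would offer a safer alternative to lumbar plexus block". The sentence before it lists what will be compared, "including time to perform the block, opioid consumption reduction, effects on postoperative pain, and the length of stay"; safety is not in that list.

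The safety premise comes from 3.1. There LPB is linked to "needle advancement into the peritoneum or retroperitoneum, which may result in a renal hematoma, vascular puncture (retroperitoneal hematoma), or even bowel puncture", while FICB is described, with a cited reference, as working "in a superficial fascial plane avoiding the potential risks of lumbar plexus block".

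The objectives (2.1) are block time, opioid consumption, pain scores and length of stay. The hypothesis (2.2) covers analgesia and time. The endpoints (4.1 and 4.2) are block time, pain scores and opioid consumption. Section 6.4, introduced by "The following data will be collected", has eight outcome items: block time, three on opioid amounts, pain scores, duration of intravenous opioids, rescue medication and length of stay. A set of demographic and surgical parameters follows.

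Section 15.1 lists common, occasional and rare effects of ropivacaine, then loss of confidentiality. Section 18.1 says only that the investigators will monitor the study.

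**The concern.** The Background gives two reasons to prefer FICB: it may be quicker, and it is taken to be safer. Speed is the primary endpoint. Safety has no variable anywhere in the plan. If 6.4 is followed as written, a vascular puncture, hematoma or organ puncture has no listed item under which it would be recorded by arm. The trial could then add nothing, for or against, to the safety part of its own rationale.

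Failed and abandoned blocks are missing too. Under 6.1 timing stops once the needle is out and the patient is positioned, so a block given up early could look like a quick one. Without a field for it, a reader of the block times could not tell.

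The third issue is internal consistency. Children are randomized to LPB, 3.1 names procedural hazards of LPB, and the risk section does not repeat them.

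**Working it through.** **Setting the sections side by side**

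| Event | Named in | In 6.4? | In 15.1? |
|---|---|---|---|
| Needle entry into peritoneum or retroperitoneum | 3.1 | No | No |
| Renal hematoma | 3.1 | No | No |
| Vascular puncture, retroperitoneal hematoma | 3.1 | No | No |
| Bowel puncture | 3.1 | No | No |
| Systemic effects of ropivacaine (seizure, cardiac arrest and others) | 15.1 | No | Yes |
| Allergic reaction | 15.1 | No | Yes |
| Failed or abandoned block | Nowhere | No | No |

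Length of stay, rescue medication and discharge destination are in 6.4 and might shift after a complication, but they would not identify one.

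**The plan's own figure**

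Section 12.2 uses a difference of 96 s, a standard deviation of 128 s, 80% power and a 95% confidence level (taken as two-sided 5%). The normal approximation gives n per group = 2(1.960 + 0.842)² × (128/96)² = 2 × 7.849 × 1.778 = 27.9, so 28. The t-test calculation gives 28.9, so 29, with power 0.801 at 29. The stated 29 reproduces. Enrolling 70 against 58 evaluable allows for 1 − 58/70 = 17% loss. The size is set by block time alone.

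**What complication data could show at this size**

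The allocation ratio is not stated; 1:1 is assumed, giving 35 per arm.

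- Upper limit with zero events, 1 − a^(1/n). For n = 35: 1 − 0.025^(1/35) = 10.0% (two-sided 95%) and 1 − 0.05^(1/35) = 8.2% (one-sided 95%). For n = 29: 11.9% and 9.8%.
- Chance of seeing at least one event in 35, 1 − (1 − p)^35. The documents give no complication rates, so p is an assumption: 3.4% at p = 0.1%, 30% at 1%, 51% at 2%, 83% at 5%.
- Comparing arms, using n per arm = [1.960√(2p̄(1 − p̄)) + 0.842√(p₁(1 − p₁) + p₂(1 − p₂))]² / (p₁ − p₂)², where p̄ is the mean of the two rates:

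| Assumed rates | n per arm for 80% power | Power at 35 per arm |
|---|---|---|
| 1% vs 0.1% | 1,059 | 7% |
| 5% vs 1% | 285 | 16% |
| 10% vs 1% | 100 | 38% |

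This approximation is rough at such low rates. Under Fisher's exact test, which 17.1 provides for according to cell size, 5 vs 0 events in 35 per arm gives p = 0.054 and 6 vs 0 gives p = 0.025. At least six events against none would be needed.

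**The case against.** A reader might infer that the trial plans to declare FICB safer on the strength of equal analgesia. The documents do not support that. Section 3.2 is a conditional sentence of rationale. Its logic is that FICB is held to avoid the LPB hazards on prior grounds (3.1), that efficacy is the open question, and that equal efficacy would make FICB the safer of two adequate options. Neither the hypothesis nor any objective or endpoint claims safety. This objection stands, and it limits the point on 3.2 to one of attribution.

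A reader might also infer that nobody is watching for harm, or that families are not told of the LPB risks. Neither follows. Section 15.1 does name serious drug effects, so only the needle-related events are absent. The data collection form and the consent form are not available to check. The health-information checklist in section 27 includes discharge, radiology and surgical reports, but which boxes are ticked cannot be read. Sections 5.2 and 11.1 add that both blocks are standard of care and in routine use at the institution. That is fair context, but it does not explain why 3.1 and 15.1 differ.

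Finally, 70 patients cannot settle a safety comparison whatever is recorded. That is correct, and it is why the added data should be labeled descriptive. It is not a reason to leave the events unrecorded.

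**Conclusion.** The point holds as a modest one. The plan lists no item for block complications or for failed or abandoned blocks, and its risk section does not carry the procedural LPB hazards that its Background names. The word *safer* in 3.2 therefore draws only on prior evidence, and the text should say so. Even with complications recorded, an arm with no events in 35 would leave rates up to 10.0% open, and power to compare arms is about 7% to 38% over the assumed rate pairs. These figures rest on 1:1 allocation and, for power, on event rates that the documents do not give. Neither the primary analysis nor the sample size is affected. This is a cheap improvement worth making, not a flaw in the primary comparison.

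**What to change.** (a) Add fields to 6.4, recorded for every patient and tabulated by arm: vascular puncture; hematoma; peritoneal, renal or bowel puncture; local anesthetic toxicity; allergic reaction; and failed or abandoned block. Apart from the last, these come from 3.1 and 15.1. Report counts with exact 95% intervals, and state that they are descriptive and that no comparative safety conclusion will be drawn from them.

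(b) In 3.2, attribute the safety statement to prior evidence and limit this trial's own conclusions to block time and analgesia. For example: *Published evidence suggests that FICB avoids some hazards of LPB; this trial compares block time and analgesia and is not designed to compare safety.*

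(c) Reconcile 15.1 with 3.1 by carrying the LPB procedural risks into 15.1, and check that the consent form agrees.

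The cost is a few tick-box fields, slightly more data entry, two wording changes and a more modest stated conclusion. No extra patients, procedures or tests are needed.
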